3. OBJECTIVES AND ENDPOINTS

Objectives	Endpoints
Primary	
To assess the efficacy of DCR-PHXC in reducing urinary oxalate burden in patients with PH	AUC from Day 90 to Day 180, based on percent change from Baseline in 24-hour Uox
Key Secondary	
To identify the proportion of participants with normalized or near-normalized Uox	The proportion of participants with a 24-hour Uox level < 0.46 mmol/24 hours or ≥ 0.46 to < 0.60 mmol/24 hours (adjusted per 1.73 m ² BSA in participants aged < 18 years) on at least 2 consecutive visits, beginning with Day 90
Secondary	
1. To evaluate the effect of DCR-PHXC on stone burden in patients with PH	1. Percent change in the summed surface area and number of kidney stones identified via kidney ultrasound from Baseline to Day 180
2. To evaluate the effect of DCR-PHXC on plasma oxalate in patients with PH	2. Percent change in plasma oxalate from Baseline to Day 180 (for adults only)
3. To evaluate the effect of DCR-PHXC on eGFR	3. Rate of change in eGFR from Baseline to Day 180
4. To assess the safety of DCR-PHXC in patients with PH	4. AE and SAE; change from Baseline in 12-lead ECG, physical examination findings, vital signs, and clinical laboratory tests
5. To characterize the PK of DCR-PHXC in patients with PH	5. Population and individual PK parameters for DCR-PHXC
Tertiary/Exploratory	
1. To evaluate the effect of DCR-PHXC on stone events in patients with PH	1. Number of stone events over a 6-month period
2. To assess the efficacy of DCR-PHXC in reducing Uox burden over 6 months in patients with PH	2. AUC of 24-hour Uox from Day 1 to Day 180, based on percent change from Baseline
3. To assess the efficacy of DCR-PHXC in reducing Uox at month 6 in patients with PH	3. Percent change in 24-hour Uox from Baseline to Day 180
4. To evaluate the effect of DCR-PHXC on urinary oxalate-to-creatinine ratio in patients with PH	4. AUC of 24-hour urinary oxalate-to-creatinine ratio from Day 90 to Day 180, based on percent change from Baseline
5. To evaluate the effect of DCR-PHXC on QoL Assessments in patients with PH	5. Change from Baseline to Day 180 in the SF-36 and EQ-5D-5L in adults; and in the PedsQL™ in children
6. To evaluate the relationship between Uox spot urine and 24-hour urine measurement in patients with PH	6. Uox in spot urine and 24-hour urine

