#### 3.2. Sample Size and Power

Approximately 40 participants will be screened to achieve an estimated total of 36 evaluable participants.

For the sample size calculations, the primary endpoint of  $AUC_{24\text{-hour } U_{ox}}$  from Day 90 to Day 180 based on percent change from baseline was used. The group sequential design with pre-specified alpha spending for interim analysis and final analysis was utilized. The randomization ratio is 2-to-1 (active-to-placebo). The primary hypothesis to be tested is a one-sided superiority hypothesis at the significance level of 0.025. The  $AUC_{24\text{-hour } U_{ox}}$  in the placebo arm is assumed to be 0, as the  $U_{ox}$  values may oscillate up and down from baseline due to measurement variability. The  $AUC_{24\text{-hour } U_{ox}}$  in the active arm is assumed to be 3600 based on a 40% decrease over the 90 days. The effect size is assumed to be 1.2. Under these assumptions, the sample size of 36 patients (24 in the active arm and 12 in the placebo arm) will yield a power of approximately 94%. All calculations were performed using [REDACTED].

The above sample size calculation was performed under the assumption that there may be an interim analysis to re-estimate sample size after two-thirds of participants complete the study. However due to late enrollment experienced in the study, an interim analysis will not be performed.

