### 8.3. Secondary Efficacy Analysis

[figure not shown]
The secondary efficacy endpoints listed below will be summarized by treatment group. A one-sided Wilcoxon Rank Sum test will be used for the comparison between treatment groups for both change and percentage change from baseline for the following outcome variables.

- Change/Percentage change from baseline to Day 180 in the summed surface area of kidney stones
- Change/Percentage change from baseline to Day 180 in the number of kidney stones
- Change/Percentage change from baseline to Day 180 in plasma oxalate (for adults only)

The stone surface area and stone count are defined as follows:

- Stone Surface Area: sum of the measured and calculated surfaces of the stone larger than 5 mm (the longest diameter)
- Stone Count: Stones will be categorized measurable or non-measurable as follows, only measurable stones will be used in the analyses:
  - Measurable : with a minimum size of 5 mm in the longest diameter the surface area of the stones
  - Non Measurable: all other stones, including small stones (longest diameter < 5 mm); if the number is too high, they may just say "too many to count", and / or provide an approximate number

Percentage change will also be calculated for the summed surface area of kidney stones and number of kidney stones using the CT results. These will be listed for each subject for the subgroup of participants from CT sub-study as described in the Protocol Appendix B.

A linear mixed model with observed eGFR as the dependent variable and treatment, study month and the interaction between treatment and month as independent variable, will be used to estimate rate of decline in eGFR response between DCR-PHXC and placebo treatments. A random intercept and slope will be included in the mixed model to fit a different intercept and slope for each subject. In this analysis nominal month will be modeled as a continuous independent factor.

The Least Squares adjusted means will be reported for each treatment group as well as the standard errors and 95% confidence intervals for the LS means. The estimate of treatment effect will be reported as the difference in treatment means, 95% confidence interval for the difference in means, the standard error for the mean difference, and the p-value for the treatment difference.

Example SAS code is provided below for reference:

```
PROC MIXED DATA= METHOD=REML;  
  CLASS <treatment> <participant ID>;  

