  MODEL <observed eGFR value> = <treatment> <Month> <treatment*Month> / SOLUTION  
  DDFM=KWR;  
  RANDOM int <Month> / SUB= <participant ID> TYPE=<covariance structure>;  
  ESTIMATE "Slope for Treatment='DCR-PHXC' " Month 1 <treatment*Month> 1 0 ;  
  ESTIMATE "Slope for Treatment='Placebo' " Month 1 <treatment*Month> 0 1 ;  
  ESTIMATE "DCR-PHXC versus Placebo" <treatment*Month> 1 -1 / alpha=0.05 CL;  
  RUN;
```

To handle the repeated measures data an unstructured variance-covariance matrix will be considered. In the event of convergence issues, a compound symmetric variance-covariance matrix will be used.

Separate ANOVA models will be considered for the following two eGFR parameters:

- Parameter 1: including all subjects using eGFR CKD-EPI equation and Schwartz et al. 2009 creatinine-based equation.
- Parameter 2: including all subjects using eGFR CKD-EPI equation and Schwarz 2012 Cystatin C-based equation

These analyses will be performed based on the ITT population. All hypotheses will be tested at the one-sided significance level alpha of 2.5% within the hierarchical testing framework described in section 6.1.4 Multiple Comparisons.

Descriptive statistics for the summed surface area of kidney stones, number of kidney stone, plasma oxalate, eGFR, and for the percent change from baseline will be presented by visit.

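### The compound-symmetric fallback for the eGFR slope model, read literally, forces the random intercept and slope to share one variance and can inflate the standard error of the slope difference several-fold

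*SAP*

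**What the plan says.** The endpoint is given in Protocol Section 3 as "Rate of change in eGFR from Baseline to Day 180". SAP 8.3 models observed eGFR on treatment, month and their interaction, and adds: "A random intercept and slope will be included in the mixed model to fit a different intercept and slope for each subject". On the time scale it says: "In this analysis nominal month will be modeled as a continuous independent factor".

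The covariance rule has two parts. The first choice is "To handle the repeated measures data an unstructured variance-covariance matrix will be considered". The fallback is "In the event of convergence issues, a compound symmetric variance-covariance matrix will be used". Neither sentence says whether the random-effects matrix or the residual matrix is meant. The example SAS code has one slot for a covariance structure: "RANDOM int <Month> / SUB= <participant ID> TYPE=<covariance structure>". It has no REPEATED statement.

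SAP 6.1.4 tests the endpoint at one-sided 0.025 as Step 6, and SAP 8.3 asks for a 95% confidence interval for the difference. The model is fitted separately for two eGFR parameters, which use different paediatric equations.

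**The concern.** Compound symmetry suits repeated measurements of one quantity, where equal variances are a natural simplification. On the RANDOM statement, the two quantities are a subject's eGFR level and that subject's monthly change. They have different units and, on any ordinary expectation, very different sizes. A single common variance must be large enough to fit the spread in level, and it then gives the slopes a large spread that the data do not show. That spread goes straight into the standard error of the slope difference.

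At stake are the interval and the test for a formally ranked secondary endpoint. In addition, if only one of the two eGFR parameters triggered the fallback, their intervals could differ many-fold for a purely computational reason.

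**Working it through.** **Figures in the plan.** The documents give no planned standard error, power or variance component for the eGFR slope. The only power statement concerns the primary AUC endpoint: "The effect size is assumed to be 1.2", and "the sample size of 36 patients (24 in the active arm and 12 in the placebo arm) will yield a power of approximately 94" percent. With 24 and 12 participants, 1/24 + 1/12 = 0.125, so the standardised difference is 1.2/√0.125 = 3.394, and Φ(3.394 − 1.960) = 92.4%. That is within two points of the stated figure. It confirms the allocation used below and has no bearing on eGFR.

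**Inputs.**
- From the documents: 24 against 12 participants; eGFR at Days 1, 30, 60, 90, 120, 150 and 180 in the Schedule of Activities, taken as months 0 to 6. The sum of squares of month about its mean is 9+4+1+0+1+4+9 = 28.
- Assumed, because the documents give only an entry floor for eGFR: intercept SD 15-30 mL/min/1.73 m², slope SD 0-2 per month, residual SD 3-8.

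**Formula, complete balanced data.** SE = √[(slope variance + residual variance/28) × 0.125]. Under compound symmetry the slope variance is replaced by the common variance v, which is approximately (intercept variance + slope variance)/2.

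**Central case: intercept SD 25, slope SD 0.5, residual SD 5.**
- Correct model: √[(0.25 + 25/28) × 0.125] = √(1.143 × 0.125) = 0.378.
- Compound symmetry: v = (625 + 0.25)/2 = 312.6, so √[(312.6 + 0.893) × 0.125] = 6.26.
- Ratio: 6.26/0.378 = 16.6.
- Half-width of a 95% interval at 1.96: 12.3 against 0.74 mL/min per month.

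REML fits to simulated trials agree. The SE is about 0.36 with an unstructured or diagonal matrix and about 5.9 with compound symmetry, where the common SD is about 17. An intercept-slope correlation of +0.3 or −0.3 leaves the ratio at about 16.

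**Dependence on the time unit.** With the same data in years, the slope SD is 6, the sum of squares is 28/144 = 0.194, and the residual term is 25/0.194 = 128.6.
- Correct model: √[(36 + 128.6) × 0.125] = 4.54.
- Compound symmetry: v = (625 + 36)/2 = 330.5, so √[(330.5 + 128.6) × 0.125] = 7.58.
- Ratio: 1.7, against 16.6 in months.

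Recoding the time axis should not alter a test. Here it does.

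**Range.** Over 48 assumed settings (intercept SD 15, 20, 25, 30; slope SD 0, 0.5, 1, 2; residual SD 3, 5, 8), the median simulated ratio of compound-symmetric to unstructured SE behaves as follows:

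| Settings | Ratio | Above 10 |
|---|---|---|
| All 48 | 3.7 to 36.6 | 27 of 48 |
| Slope SD 0 | 5.8 to 36.6 | 10 of 12 |
| Slope SD 2 | 3.7 to 10.9 | 1 of 12 |

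Outside this grid, with intercept SD 10, slope SD 1 and residual SD 8, the simulated ratio is only 1.5.

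**Can the fallback be triggered?** In 2,000 simulated complete-data trials per setting (intercept SD 15-25, residual SD 5-8), the unconstrained estimate of the intercept-slope matrix was not positive definite in 54-59% of trials at slope SD 0-0.1, 46-53% at 0.25, 23-44% at 0.5 and 1-15% at 1.0. A repeat of this check gave the same pattern, within about two percentage points. Such an estimate often produces a warning. It does not always stop the fit.

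**The other reading.** If compound symmetry was meant for the residual matrix in place of the random effects, the model is equivalent to a random intercept alone. Its SE is then 0.47 to 1.00 of the unstructured SE on the same grid, and is too small when slopes truly vary.

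**The case against.** The strongest reply is that the text is ambiguous. It introduces the matrices as a way to handle repeated measures, which usually means within-subject covariance, and the code is offered only as an example with a placeholder. On a residual-matrix reading nothing is inflated. This stands as a reason to clarify, but it does not rescue the rule: that reading drops the random slope that SAP 8.3 specifies and understates the SE when slopes vary. The code, the only place where the structure is located, supports the literal reading.

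A reader might infer that the fallback always inflates the SE more than ten-fold. The documents do not support this. The factor rests on variance components that they do not state, and falls below ten in 21 of the 48 assumed settings. One plausible case (20, 1.0, 5 for intercept, slope and residual SD) gave 4.72/0.48 = 9.8 in a small simulation. The factor would also shrink if the model carried the baseline eGFR covariate that Protocol 9.5.1 names and the SAP code omits.

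Nor do the documents establish that the unstructured fit will fail. The rates above show only that a problem estimate is common when slopes barely vary, and the SAP does not define a convergence issue.

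Finally, it is fair to say that the error is conservative. With complete balanced data the slope estimate is unchanged, so a literal compound-symmetric fit loses power and does not create false positives. Step 6 leads to no further test.

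**Conclusion.** The fallback is wrong as written. Taken literally from the code, it equates variances in different units, makes the result depend on how time is scaled, and inflates the SE of the slope difference by about 4- to 37-fold under the assumed ranges. The inflation tends to be worst when slopes hardly vary, which is also when the unstructured fit is most likely to give trouble.

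The direction and the unit-dependence follow from the specification. The size depends on assumed SDs and on complete, balanced data. The consequence is confined to the eGFR slope comparison: a far too wide interval and a test with little power, and only if the fallback is used. The primary analysis and the other ranked secondary tests are not affected. This should be corrected before unblinding, but it does not threaten the trial's main conclusion.

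**What to change.** In SAP 8.3, state that the covariance structure applies to the random-effects matrix of intercept and month. Replace the compound-symmetric fallback with separate, uncorrelated intercept and slope variances (TYPE=VC or UN(1) on the RANDOM statement). If the slope variance is then estimated as zero, use a random intercept only, and report that this was done. It would also help to say what counts as a convergence issue, including whether a random-effects matrix that is not positive definite qualifies.

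The cost is a sentence or two in the SAP, with no change to data collection. In the central case the diagonal matrix gives the same SE as the unstructured one (about 0.36 each). There are two small downsides. The diagonal form sets the intercept-slope covariance to zero, and the random-intercept-only model can understate the SE if slopes truly vary. For that reason it belongs last in the sequence and should be disclosed when used.

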#### 8.4. Tertiary/Exploratory Efficacy Analysis

The same statistical model described above for the primary efficacy analysis will be applied to the following tertiary/exploratory efficacy endpoints.

- AUC24-hour Uox from Day 1 to Day 180, based on percent change from baseline (ITT population)
- Percent change in 24-hour Uox from baseline to Day 180 (ITT population)
- AUC24-hour Uox:creatinine from Day 90 to Day 180, based on percent change from baseline (MITT population)
- Change from baseline to Day 180 in the SF-36, EQ-5D-5L in adults, and in the PedsQLTM in children (ITT population)

The number of stone events over a 6-month period will be analyzed using an exact Poisson regression model. The model will include treatment group and baseline stone events rate (continuous). Baseline stone events rate will be the number of stone events observed over the past 12 months prior to dosing. The model will include an offset term for total follow-up time as the 'number of months exposed' equal to the total elapsed time between first dose date and last day of visit in the study, divided by 30.4375. Annualized stone event rate (number of stone events per year per person) will be derived as number of stone events in the exposure period / total number of years exposed.

Example SAS code is given below:

```
PROC GENMOD DATA=;  
  CLASS TREATMENT;  
  MODEL 'Number_stone_evts_6month'=Treatment Kidney_Stone_Event_Baseline  
/OFFSET=Ln_Number_Of_Months_Exposed DIST=POISSON LINK=LOG DSCALE;  
  EXACT Treatment Kidney_Stone_Event_Baseline / ESTIMATE;  
RUN;
```

The number of stone events will be calculated as the number of discreet (non-concurrent) adverse events marked as a Kidney Stone Event on the adverse event CRF. Kidney stone events include: renal stone requiring medical intervention, stone passage with or without hematuria, and renal colic requiring medication. Concurrent events will be defined as events occurring within the same 4-week (28-day) window. For example, renal colic treated with medication on Monday 12 November 2019 followed by stone passage without hematuria on Friday 30 November 2019 is a single (concurrent) stone event (18 days between start and stop of single stone event). Renal colic treated with medication on Monday 12 November 2019 followed by stone passage without hematuria on Wednesday 13 December 2019 is considered two separate stone events (30 days between discreet event one and event two).

To evaluate the relationship between Uox in spot urine and 24-hour urine, the correlation between the two measurements will be examined for the ITT population.

Descriptive statistics for SF-36 and EQ-5D-5L scores in adults, PedsQL scores in children, and Uox in spot urine samples, and the percent change from baseline will be presented by visit.

## 8.5. Sensitivity Analyses

The following sensitivity analyses will be performed for the primary endpoint:

- Same analysis as described in Section 8.1, but performed on the ITT population.
- Same analysis as described in Section 8.1, but performed on the EVAL population.
- Non-parametric analysis of the primary endpoint ( $AUC_{24\text{-hour } U_{ox}}$ ) using Wilcoxon Rank Sum test for the comparison between treatment groups
- Same analysis as described in Section 8.1, but performed on BSA adjusted Uox concentration for all participants.
- Same analysis as described in Section 8.1, but rather than using the mean of the two screening 24-hour Uox values as the baseline value the lowest of the two screening 24-hour Uox values.
- Same analysis as described in Section 8.1, but using all Uox concentrations, including those which do not meet completeness criteria (see section 6.1.5.2)
- Same analysis as described in Section 8.1 but performed using an MI approach assuming that the data are missing not at random (MNAR). Control-based pattern imputation will be used together with FCS. Control-based pattern imputation explores the assumption that patients revert to control group after drop-out. Thus, it is assumed that after drop-out, the unobserved values in experimental group follow the path of observed values in control group.

Section 6.1.5.1 describes the details of the MI approach used in the primary analysis using MAR. For this sensitivity analysis, Step 1 of section 6.1.5.1 will be replaced with the following:

- Step 1: The MNAR imputation model will impute missing values using an FCS regression-based multiple imputation model.

The further description of step 1 still applies, the SAS pseudo code will be amended using additional MNAR statement within PROC MI:

```
MNAR model (<day 90> <day120> <day 150> <day 180> / modelobs=  
(<treatment> ='Placebo'));
```

- Same analysis as described in Section 8.1 but performed without using an MI approach

## 9. Safety and Tolerability Analysis

Safety will be evaluated from reported AEs, reported concomitant medications, changes in clinical laboratory values, changes in vital signs, electrocardiogram (ECG), echocardiogram with Doppler, and physical examination results.

All safety analyses will be performed on the SAF population. All summaries will be descriptive in nature. No statistical comparisons will be performed.

## 9.1. Adverse Events

All AEs, TEAEs, and SAEs will be coded using the MedDRA v23.0 or higher. AEs will be classified as treatment-emergent for analysis in summary tables where applicable.

A TEAE is defined as any event that started, changed in intensity, or changed relationship to the study treatment at the time of or after the first dose date and through the study completion date.

An overview summary of AEs, including counts and percentages, the risk difference and their 95% CI will be presented for subjects with: any TEAEs, TEAEs related to study treatment; TEAEs leading to treatment discontinuation, treatment-emergent SAEs, treatment-emergent SAEs related to study treatment, TEAEs of special interest (i.e., injection site reactions; muscle pain or weakness; kidney stones: renal stone requiring medical intervention, stone passage with or without hematuria, and renal colic requiring intervention), and fatal TEAEs.

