8.3.1. Time Period and Frequency for Event Assessment

All SAEs will be collected from the signing of the ICF until 30 days after the last day of study participation.

All AEs will be collected from the signing of the ICF until the EOS at the time points specified in the SoA (Section 1.3).

Any medical condition that is present at the time that the participant is screened will be considered as baseline and not reported as an AE. However, if the study participant's condition deteriorates at any time during the study, it will be recorded as an AE.

Investigators are not obligated to actively seek AE or SAE after conclusion of the study participation. However, if the Investigator learns of any SAE, including a death, at any time after a participant has been discharged from the study, and he/she considers the event to be reasonably

related to the study intervention or study participation, the Investigator must notify the Sponsor promptly.

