- kk. Adverse events to be collected from the time of ICF signature through the End of Study/Early Termination Visit. Participants will be questioned as to the occurrence of muscle pain or weakness.

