### 6.1.9. Derived Variables

Change from baseline = value at current time point – baseline value

$$\text{Percentage change from baseline} = \left( \frac{\text{value at current time point} - \text{baseline value}}{\text{baseline value}} \right) * 100\%$$

Treatment-emergent AE (TEAE) = any AE with an onset date/time on or after administration (including any partial administration) of the first dose of study intervention and through the study completion date from the end of study CRF. That is, if the start time for the AE is provided, then the AE start date and time will be compared with the first dose date and time in order to determine whether the AE is a TEAE. If the start time for the AE is not provided, then the AE start date will be compared with the first dose date. In this case if the AE start date is on or after the first dose date, then the AE is considered a TEAE.

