### 9.1.1. Adverse Events Summaries

The number and percentage of participants with AEs will be summarized by SOC and PT. This summary will further be tabulated by strongest relationship to study intervention (related: definitely, probably, and possibly related; unrelated: unrelated; missing). A similar summary of TEAEs will be produced by maximum intensity (mild, moderate, severe, missing). In addition, the number and percentage of participants who experienced non-serious TEAEs (all TEAEs except serious TEAEs) that occurred in more than 5% of participants in either treatment group will be presented by SOC and PT for each treatment.

To count the number of participants who experienced each TEAE, a participant experiencing the same TEAE multiple times will only be counted once for the corresponding PT. Similarly, if a participant experiences multiple TEAEs within the same SOC, the participant will be counted only once for that SOC. For summaries by maximum severity, if a participant experiences more than one TEAE with different intensities severity (e.g., the same SOC and PT), only the worst intensity/severity will be reported. If a participant has both missing and non-missing intensity for a given SOC and PT, the missing intensity is selected for reporting unless the non-missing severity is noted as Severe. Treatment-emergent AEs will be sorted alphabetically by SOC and PT and presented by decreasing order of overall frequency. Treatment-emergent AEs analyzed by strongest relationship will be selected similarly for participants experiencing more than one TEAE with different relationships. If a participant has both missing and non-missing relationship for a given SOC and PT, the missing relationship is selected for reporting unless the non-missing relationship is noted as Related.

The number of TEAEs will be presented by SOC and PT. The total number of TEAEs will also be presented in the display.

In addition, all TEAEs will be provided in a listing, which will include the participant identifier, study intervention start date/time, SOC, PT, verbatim term, intensity, seriousness, relationship, action taken, outcome, date/time of onset, study day, date/time of resolution, and event duration in days. Event duration will be calculated as: (resolution date – start date) +1.

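### The SAP carries two definitions of a treatment-emergent AE that disagree for events starting before the first dose, and does not say which governs

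*SAP*

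**What the plan says.** SAP section 6.1.9 (Derived Variables) gives an onset rule. A TEAE is "any AE with an onset date/time on or after administration (including any partial administration) of the first dose of study intervention", up to study completion. Where a start time is recorded, "then the AE start date and time will be compared with the first dose date and time in order to determine whether the AE is" treatment-emergent; where none is recorded, dates alone are compared. Intensity and relationship play no part. The partial-date rules in SAP section 6.1.10.1 have the same basis: an AE whose start month precedes the month of first dose, in the same year, is treated as not potentially treatment-emergent.

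SAP section 9.1 (Adverse Events) gives a second definition: "A TEAE is defined as any event that started, changed in intensity, or changed relationship to the study treatment". The start or change has to fall, in that section's words, "at the time of or after the first dose date and through the study completion date". The reference here is the first dose date, with no comparison of clock times.

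No text ranks one above the other. Protocol section 9.5.2 summarises AEs, SAEs and AEs leading to withdrawal without settling the matter, and SAP section 10 records no changes from the planned analysis.

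The flag feeds visible outputs. Section 9.1 plans: "An overview summary of AEs, including counts and percentages, the risk difference and their 95% CI will be presented for subjects with: any TEAEs", followed by further TEAE categories. Section 9.1.1 adds: "The number of TEAEs will be presented by SOC and PT".

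**The concern.** Pre-dose AEs will exist in the database, because the SAP's schedule of events (Table 1) has "Adverse events to be collected from the time of ICF signature through the End of Study/Early Termination Visit". An AE that begins in screening and changes after Day 1 is a TEAE under section 9.1 and not under section 6.1.9. Two programmers working from the same SAP could therefore produce different TEAE counts, percentages and risk differences.

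The wording of 9.1 has two further defects. Change in intensity has no direction, so a pre-dose event that improves after dosing becomes treatment-emergent. A changed causality rating is also enough, so an event re-rated as unrelated after Day 1 becomes treatment-emergent with no clinical change at all.

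What is at stake is the reproducibility of the AE tables. The SAP presents itself as a plan fixed before database lock; a definition chosen after unblinding would be an avoidable analyst choice in the safety results.

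**Working it through.** The plan states no figure for this point, so there is none to reproduce. The check is a comparison of the texts, then the size of a single reclassification.

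**Step 1. The two definitions side by side.**

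| Event | 6.1.9 | 9.1 |
|---|---|---|
| New AE after first dose | TEAE | TEAE |
| Condition present at screening, deteriorates after dosing, recorded as an AE with its own onset | TEAE | TEAE |
| AE starts between consent and first dose, unchanged later | not | not |
| Same, worsens after dosing | not | TEAE |
| Same, improves after dosing | not | TEAE |
| Same, only the causality rating changes | not | TEAE |
| AE on Day 1 with a recorded start time before the dose | not | can be a TEAE, on the date wording |

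The disagreement is confined to the last four rows.

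**Step 2. Can such events arise?** The schedule of activities allows up to 2 weeks from consent to the first screening procedure, then up to 35 days of screening, or 60 under Protocol Appendix A. The pre-dose AE window can reach 14 + 35 = 49 days, or 14 + 60 = 74 days, before any 7-day extension. Protocol section 10.3.4 allows the investigator to revise causality on follow-up, and has new information entered on the original CRF record. That suggests a pre-dose AE keeps its pre-dose onset when it changes. On Day 1 there are blood draws before dosing, so an AE timed before the dose is possible.

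**Step 3. Size of one reclassification.** Inputs: planned arm sizes of 24 active and 12 placebo (SAP section 3.2). A participant who has a TEAE in a category under one definition only, and no other TEAE in that category, moves the arm's proportion by 1/n:

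- active: 1/24 = 4.2 points
- placebo: 1/12 = 8.3 points

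Illustration with a Wald 95% interval, RD ± 1.96 × √[p₁(1−p₁)/24 + p₂(1−p₂)/12]. The starting counts are assumed and do not come from the documents.

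| Active | Placebo | Risk difference (points) | 95% CI |
|---|---|---|---|
| 12/24 | 6/12 | 0.0 | −34.6 to 34.6 |
| 13/24 | 6/12 | 4.2 | −30.4 to 38.8 |
| 12/24 | 7/12 | −8.3 | −42.7 to 26.0 |

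**Step 4. The reporting threshold.** SAP section 9.1.1 tabulates non-serious TEAEs seen in more than 5% of either group. At planned sizes one placebo participant (8.3%) crosses that line; in the active arm the second does (2/24 = 8.3%, against 4.2% for one). A single reclassification can decide whether a preferred term appears.

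Event counts by SOC and PT differ for each affected AE, whether or not the participant has another.

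**The case against.** The best defence is that the operational text points one way. Only section 6.1.9 gives a rule that can be programmed, and section 6.1.10.1 agrees with it. The TEAE listing in section 9.1.1 has one onset, one intensity and one relationship field, with no date of change. On that view 9.1 is loose wording and onset would be used in practice. This makes a divergence less likely but does not remove it: 9.1 is the section that introduces the AE tables, it states its definition outright, and the CRF is not among the documents.

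A reader might infer that the onset rule would hide worsening stone disease on treatment. The documents do not support that. Under Protocol section 8.3.1 a condition present at screening is baseline, but if the participant's "condition deteriorates at any time during the study, it will be recorded as an AE". Protocol section 10.3.1 also counts exacerbation of a pre-existing chronic or intermittent condition as an AE. Such a record would normally carry a post-dose onset and count under both definitions. Stone events are captured separately as discrete AEs under a 28-day rule. This part of the defence stands, and it limits the gap to AEs that newly arise after consent.

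A reader might also infer that nearly every safety table is affected. Laboratory, vital-sign, ECG, echocardiogram, physical-examination and concomitant-medication summaries do not use TEAE status, and the first SOC/PT summary in 9.1.1 is worded for AEs in general. Nor is any hypothesis test touched, since SAP section 9 makes all safety summaries descriptive.

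Finally, any single definition would cure the contradiction; including worsening is a recommendation beyond that.

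**Conclusion.** The contradiction is real and minor. Sections 6.1.9 and 9.1 classify the same event differently when an AE starts between consent and first dose and later changes in intensity or relationship, or when a Day 1 AE is timed before the dose. Most AE tables and the overview risk differences depend on the flag.

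The shift of 4.2 or 8.3 points per participant assumes the planned 24 and 12 as Safety Population denominators and no other TEAE in the category for that participant. The number of such participants cannot be derived from the documents and may be small or nil. That pre-dose AEs keep their original onset when they change is an inference from Protocol section 10.3.4, since the CRF is not available. Efficacy conclusions and type I error are unaffected.

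**What to change.** Keep one definition, in SAP section 6.1.9, and have section 9.1 refer to it. Suggested content: onset on or after the first dose, judged by date and time where a time is recorded; or onset before the first dose with worsening in intensity after it. Remove the relationship limb and the undirected change in intensity.

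State how worsening is identified: from dated intensity changes on the CRF, or from a new AE record with its own onset. The documents describe no dated change, so this must be checked before the text is fixed. Amend the partial-date rule in section 6.1.10.1 so that an AE with a pre-dose start month is not ruled out when a later worsening is documented.

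The cost is a short SAP edit in three sections and one revised derivation, plus a data-entry instruction if the CRF lacks dated intensity changes. It should be done before unblinding.
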